AB to drug cues has also been associated with treatment outcome. Among the substance dependent, AB has been associated with treatment compliance [38] and treatment outcome [24–28]. AB, in the form of a smoking Stroop task given on the first day of quitting, was found in one study to be a better predictor of smoking cessation outcome than traditional measures of dependence [28]. Pre-treatment AB to a heroin Stroop task was found to predict 3-months post-treatment relapse status in heroin users attending an inpatient treatment center [27]. In a sample of alcoholics undergoing in-patient treatment, patients who later relapsed after discharge were found to produce increased AB on an alcohol Stroop task given during day 1 and week 4 of treatment, while non-relapsers and controls showed a decrease in AB during that time period [25].

ABM reduces AB to drug-related cues. The theoretical and empirical support for the association between AB and substance use has led many to pursue research into directly altering AB using ABM. ABM for substance abuse developed out of interventions designed to reduce AB in individuals with anxiety, given that a hallmark of anxiety disorders is an AB towards threat-related stimuli [39–41]. The majority of ABM interventions involve a modified visual probe task [42]. The classic visual probe task, used to assess AB, is a measure of visual attention where a pair of photographs, one bias-related (i.e., drug-related) and one neutral, are briefly presented simultaneously on a screen. After both pictures are removed from the screen, a small visual probe is presented in the former location of one of the pictures, with participants instructed to respond to the probe as quickly as possible with a button press. Each picture is probed an equal number of times. Drug dependent participants consistently respond faster to probes occurring in the place of drug-related pictures compared to neutral pictures, including smokers [43], heavy drinkers [44], and the opiate dependent [16], suggesting that drug-related stimuli capture attention in those with drug problems. In the modified visual probe task, used to deliver ABM interventions, the majority or all of the probes replace neutral pictures. This task trains participants to attend to neutral pictures and away from drug-related pictures.

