We have experience evaluating AB in smokers using RT tasks. For example, in one study we examined whether AB to smoking words, as measured by the smoking Stroop task, was associated with the motivational salience of smoking pictures, as measured by peripheral physiology [58]. Scores for the smoking Stroop and for the peripheral physiology, including zygomaticus major ("smile muscle") electromyography (EMG), corrugator supercilii ("frown muscle") EMG, heart rate (HR) and skin conductance (SC), were created by taking a difference score for each measure by subtracting the responses to the neutral from the smoking stimuli. Smokers who had slower RTs to smoking words produced larger zygomaticus major EMG to smoking cues than those with faster RTs. However, scores on the smoking Stroop were unrelated to the corrugator supercilii EMG, HR, or SC responses to smoking stimuli. These results suggest that AB to smoking cues is more strongly associated with appetitive motivational measures (i.e., zygomaticus major activity) than with measures of avoidance (i.e., corrugator supercilii activity) or measures of physiological arousal (i.e., HR, SC). This is consistent with theories that smoking cues are associated with conditioned responses that capture attention, and are consistent with other work from our lab [59,60].

We have experience assessing in-home AB in smokers trying to quit. As part of an Ecological Momentary Assessment (EMA) study, we had 119 community smokers carry around a personal data assistant (PDA) during the first week following their scheduled quit attempts [61]. As part of multiple planned and random assessments per day, participants recorded their craving to smoke and completed a modified Stroop task, a measure of AB to smoking words. Overall, the smokers produced a significant smoking Stroop effect, (17.9 ms, $SD=46.6$; $t[118]=4.19$, $p<.0001$, Cohen's $d = 0.38$), indicating AB to smoking words, and the smoking Stroop effect was positively correlated with craving ratings, $r(117)=.28$, $p<.01$. These results demonstrate that reliable and significant AB can be captured on a hand-held device in a participant's day-to-day environment, and that this AB is associated with self-reported craving.

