occurs in place of one them until a button is pressed, or until 1000 ms has passed. Participants will be instructed to press a button corresponding to the side of the screen (left or right) where the probe appears. Incorrect responses, or responses that occur outside of 20-1000 ms interval after probe onset, will result in the word "incorrect" appearing on screen in red for 2000 ms. The laboratory AB assessment will consist of 16 picture pairs repeated 10 times over four blocks, for a total of 160 trials. Every picture pair will be probed, with random probes following each picture or word an equal number of times, and each picture or word randomly located on the left and right of the screen equally often. After each block of 40 trials, participants will receive feedback on their performance, including accuracy and mean RT, and be instructed to relax for 20 s before the start of the next block. An on-screen tally of money earned and lost will also appear as part of this feedback, with participants gaining \$0.025 for each correct response within the response window (\$4 maximum). An AB score will be calculated by taking the mean RT difference between the CIG and NEU targets on trials with correct responses within the response window [7,91]. As part of the exploratory data analyses, participants' eye movements will also be tracked using the Tobii TX-300 eye tracking system developed by Tobii Technology, Inc. during a paired picture-viewing task. Eye movement data will be used to supplement RT data collected during the MDP, because recent studies of attention-bias for both alcohol [92] and tobacco [93] use disorders have called into question the reliability of reaction time as the primary outcome measure of AB. Laboratory sessions, including smoking behavior and ERP assessments, will be conducted by a laboratory technician and overseen by PI [name], and co-I [name], experts in using electrophysiology to study attentional and affective processes. The laboratory AB assessment will last approximately 10 min. Prior to beginning the first MDP task, the Self-Assessment Manikin (SAM) will be administered to allow participants to rate the images used in the experiment on the dimensions of affective valence and arousal [94].

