Laboratory sessions: AB assessment using the modified Stroop task. In order to determine generalizability of ABM training across stimulus modalities, participants will complete a modified Stroop task designed to evaluate AB to smoking words [28]. The modified Stroop task is predictive of relapse in nicotine-, alcohol-, and heroin-dependent individuals [25,27,28]. Participants will be told that a series of words will appear on the screen in different colors, that they should press a button on the response box corresponding to the color of the text used to present the word, and that they should respond as quickly and accurately as possible. The monetary rewards associated with quick and accurate performance will also be explained. Participants can earn \$0.025 for each correct response, within the response window, in the neutral and smoking blocks (\$4 maximum). The Stroop task will consist of three blocks, with a 5-s rest period between blocks: (a) practice (40 trials), (b) neutral words (80 trials), and (c) smoking words (80 trials). The neutral block will be presented before the smoking block to avoid carryover effects [28]. Each trial will begin with a fixation cross at the center of the screen for 500 ms, functioning as the ITI. After the ITI, the fixation cross will disappear and a word will be presented in its place using one of four text colors: red, green, blue, or yellow. The word will remain on the screen until the participant responds, for a maximum of 3 s. During the practice block, if the participant makes an error, or does not respond within 3s, a notification will be rapidly flashed on the screen for 200 ms. The practice stimuli will be 10 repeated letter strings (e.g., HHHHHH, XXX). The neutral stimuli will be 20 neutral words (e.g., ARRIVAL, CLOCK). The smoking stimuli will be 20 smoking-related words (e.g., SMOKE, PUFF). Each word will be presented four times per block, once in each color. The words will be delivered in a random order with the following restrictions: Each word will appear once in each sub-block of 20 consecutive trials (10 trials for the practice block), and the same color will not appear on two consecutive trials. An AB score will be calculated by taking the mean RT difference between the smoking and neutral words on trials with correct responses within the response window. The Stroop task will take approximately 7 min to complete.

[figure not shown]

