
Statistical Approach & Expected Outcomes

Aim 1. Identify the impact of in-home ABM on AB. We will evaluate this aim using 2 (group: ABM vs. sham) X 3 (session: baseline, 1-day post-training, and 8-weeks post-training) linear mixed model using RT difference scores (neutral-cigarette) as the dependent measures and subject as the random effect. We will conduct separate analyses on the dependent measures (within-modality: MDP RT difference scores; between-modality: Stroop RT difference scores) collected at baseline, 1-day post-training, and 8-weeks post-training. We predict that post-training AB scores, calculated from RT, will decrease from baseline for those in the ABM training, but not in the sham training condition, indicating a reduction in AB to smoking cues.

Aim 2. Identify the impact of in-home ABM on smoking behavior. We will evaluate this aim using two types of models. For the continuous (i.e., normally distributed) measures of smoking behavior, we will conduct mixed between-within repeated measures ANOVA using the same predictors and covariates as are described in Aim 1. Separate analyses will be run for each of the continuous dependent measures, including mean CPD over the past 7 days, expired CO, cotinine, FTND, and WSWS Craving. We expect that ABM training, compared to sham training, will decrease measures of smoking exposure (CPD, expired CO, cotinine), levels of dependence (FTND), and levels of craving (WSWS Craving) at the 1-day and 8-weeks post-training sessions. For the categorical variable of 8-weeks post-NRT abstinence, we will conduct a chi-square test of independence on the 2 (abstinent vs. nonabstinent) x 2 (ABM vs. sham training) table. We expect that ABM training, compared to sham training, will result in a higher rate of abstinence.

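### Aim 1 scores both tasks as neutral minus cigarette and reads a fall as less bias, which is right for the dot-probe and reversed for the Stroop

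*Combined protocol and SAP*

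**What the plan says.** Under Statistical Approach & Expected Outcomes, Aim 1 is a 2 (group) by 3 (session) "linear mixed model using RT difference scores (neutral-cigarette) as the dependent measures and subject as the random effect". The dependent measures are then named as "within-modality: MDP RT difference scores; between-modality: Stroop RT difference scores", each analysed separately. The prediction is that AB scores will "decrease from baseline for those in the ABM training, but not in the sham training condition, indicating a reduction in AB" to smoking cues. One subtraction order, one predicted direction and one interpretation cover both tasks, with no exception.

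The task descriptions do not give a sign. For the dot-probe the AB score comes from "taking the mean RT difference between the CIG and NEU targets"; for the Stroop, from "taking the mean RT difference between the smoking and neutral words". Neither says which mean is subtracted from which.

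Two background passages show how bias appears in each task:

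- **Dot-probe** (Justification & Feasibility): drug-dependent people "consistently respond faster to probes occurring in the place of drug-related pictures compared to neutral pictures".
- **Stroop** (Preliminary Studies): the team's earlier smoking Stroop score was formed "by subtracting the responses to the neutral from the smoking stimuli", with the finding that "Smokers who had slower RTs to smoking words produced larger zygomaticus major EMG to smoking cues than those with faster RTs".

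**The concern.** Bias speeds responses in the dot-probe, because attention is already where the probe appears. It slows them in the Stroop, because the meaning of the word interferes with naming its colour. A score built with one subtraction order therefore has opposite meanings in the two tasks.

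If the analysis text is followed literally, a true Stroop benefit appears as an increase, against the stated prediction, and a worsening appears as the predicted decrease. The Stroop is the between-modality outcome and carries the Aim 1 hypothesis that training effects carry over to another type of stimulus, so the direction of that result could be misreported. A significant group-by-session interaction does not by itself show which arm improved; the reader relies on the sign convention for that.

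There is a secondary consequence. The in-home AB assessment uses only the Stroop and takes over the laboratory definition. The exploratory analyses of optimal training length and of baseline AB as a predictor of response also need a stated Stroop sign.

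**Working it through.** **Step 1. Sign of the score when bias is present.** Let N be the mean RT for the neutral condition and S the mean RT for the smoking condition.

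- Dot-probe: bias means S < N (Justification & Feasibility), so N − S > 0. Less bias moves N − S down toward 0.
- Stroop: bias means S > N. This is inferred from Preliminary Studies. The score there is smoking minus neutral, slower smokers on smoking words had the larger zygomaticus response, and the authors conclude that AB goes with that response. Slower is therefore being read as more AB. Hence N − S < 0, and less bias moves N − S up toward 0.

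**Step 2. Does a decrease mean less bias?**

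| Order used for both tasks | Dot-probe | Stroop |
|---|---|---|
| Neutral minus smoking (Aim 1 text) | yes | no |
| Smoking minus neutral | no | yes |

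Neither single order works for both tasks.

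**Step 3. The plan's own Stroop figure.** Preliminary Studies reports a Stroop effect of 17.9 ms, SD 46.6, t[118] = 4.19, d = 0.38. With n = 119:

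- t = 17.9 / (46.6/√119) = 17.9 / 4.27 = 4.19
- d = 17.9 / 46.6 = 0.38

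Both reproduce. This confirms the figures but not the sign, because the arithmetic is the same whichever order produced 17.9 and the text does not state the order. The sign argument rests on the other Stroop study quoted above.

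**Step 4. Size of the reversal (illustration).** If Stroop bias is b ms and training removes a fraction p of it, N − S goes from −b to −(1 − p)b, a change of +pb.

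- b assumed 5 to 25 ms, p from 0.5 to 1: from 0.5 × 5 = +2.5 ms to 1 × 25 = +25 ms.
- b = 17.9 ms: 0.5 × 17.9 ≈ +9.0 ms to +17.9 ms.

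The plan predicts a decrease in every one of these cases. The 17.9 ms came from hand-held testing in the week after a scheduled quit date, so it is not this trial's expected baseline.

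**Step 5. Effect on the test.** Replacing Y by −Y changes each group-by-session coefficient from β to −β and leaves its standard error alone, so the Wald or F statistic, p-value, effect size and power are unchanged. One simulated Stroop data set agrees. It assumed 250 participants split 1:1, three sessions, SD 46.6 ms, within-subject correlation 0.5, and 17.9 ms of bias fully removed in the ABM arm. The interaction chi-square was 17.93 on 2 df (p = 0.00013) under both orders. The two contrasts were +23.4 and +17.7 ms as neutral minus cigarette, and −23.4 and −17.7 ms as smoking minus neutral.

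**Step 6. Would the baseline data reveal the sign?** Taking SD 46.6 ms as an assumption for this trial, the standard error of the baseline mean at N = 250 is 46.6/√250 = 2.95 ms. A bias of 5 ms gives t = 5/2.95 = 1.7, and 25 ms gives t = 8.5. At the low end of the assumed range the baseline mean would not settle which sign denotes bias.

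**The case against.** The strongest reply is that this is loose drafting with little consequence. The hypotheses are stated as a reduction in bias, not as the sign of a number, and the team has already scored a smoking Stroop as smoking minus neutral. The term AB score is defined separately for each task in the laboratory sections, so the parenthesis in Aim 1 may be dot-probe shorthand, or its hyphen may only label a contrast. No one-sided test or success rule depends on the sign, and the scores can be recomputed. In addition, the plan nowhere says outright that slower responses to smoking words are the bias, and the smartphone analyses are exploratory and state no order.

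Much of this stands. The inferential results are unaffected, the error is reversible, and the Stroop direction is inferred, though from a clear passage. The smartphone point is a missing detail rather than the same error.

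The milder reading does not repair the text. The laboratory definitions give no sign. Both name the smoking stimulus first, so reading them as smoking minus neutral would fix the Stroop only by contradicting the order written in Aim 1, and would put the dot-probe definition in conflict with Aim 1 as well. Knowing what the team probably means is no substitute for a stated rule: with the literal text and the team's earlier convention opposed, a Stroop effect in either direction could be called consistent with the plan.

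**Conclusion.** The concern holds. As written, the Aim 1 score is correctly oriented for the dot-probe and reversed for the Stroop. One of the two Aim 1 outcomes is affected, in predicted direction and interpretation only; the p-value, effect size and power stay the same. The conclusion rests on the plan's own account of how bias shows in each task and on reading the Aim 1 parenthesis as a subtraction that applies to both measures named after it. The millisecond figures illustrate the reversal under assumed bias sizes and are not needed for the conclusion. It should be corrected before analysis because the Stroop carries the cross-modal claim.

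**What to change.** In the Aim 1 analysis text, define the score for each task:

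- MDP AB = mean RT with the probe at the neutral picture minus mean RT with the probe at the smoking picture.
- Stroop AB = mean RT to smoking words minus mean RT to neutral words.

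Add that a higher score means more bias toward smoking cues in both tasks. The predicted decrease is then right for both and can stay. Put the same signed definitions in the two laboratory task descriptions, and state that the in-home Stroop and the exploratory analyses that use AB follow the same sign.

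The cost is one sentence in the analysis section and matching edits in the task descriptions. Data collection, sample size and the statistical test do not change.

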Study overview. Participants will be 250 community smokers, currently interested in quitting smoking, who will be randomly assigned (stratified by gender) to receive either ABM or sham training. Smokers in both groups will attend three laboratory sessions (Figure 2). The first lab session will establish each smoker's baseline smoking behavior and AB towards smoking picture and word cues by assessing reaction time (RT) and event-related potential (ERP) electroencephalography to modified dot-probe (MDP), Stroop color-word naming tasks and a passive picture viewing task. After the first lab session, participants will complete 13 days of daily in-home training (ABM or sham) and AB assessments that will be administered through a provided smartphone, with compliance and accuracy rewarded monetarily. The second lab session will occur the day after the final day of in-home training and will involve the same assessments as the first session, to gauge the short-term impact of ABM on AB and smoking behavior. At the end of the second lab session, participants will have a 30-minute counseling session with a smoking cessation counselor and be given the first half of an 8-week supply of NRT. The participants will be instructed to quit the next day, and will have 3 biweekly phone counseling sessions while on NRT. After participants complete one biweekly phone counseling session, they will be mailed the remainder of their 8-week supply of NRT. Participants will be given a window of seven days after the scheduled date of their second lab session to complete the session. The final lab session, which will occur 8 weeks after the second session, will measure the longer-term impact of training on smoking behavior and AB. Participants will be given a window of fourteen days after the scheduled date of their final lab session to complete the session. Out of window visits will be noted in the progress notes but will not be considered a protocol deviation. Visit 3 has a window with an ending period of whenever final abstinence data is collected or the trial ends, whichever is sooner. A study staff member will make attempts to contact participants who miss Visit 3 until the end of the study or until the participant requests no further efforts be made to contact them. For those who miss Visit 3, a study staff member will call them to invite them to come in as originally planned so that abstinence (e.g., TLFB assessment since last contact, CO, urine cotinine, and anabasine), and lab data can be collected. If participants are unable to attend Visit 3, staff will ask participants to complete TLFB over the telephone to record CPD since last visit. Staff also will offer to send participants' questionnaires via email. If smoking abstinence is reported, staff will invite participants to come in or will offer to send them a NicAlert or comparable urine cotinine test to biochemically verify abstinence. Participants will be asked to send a picture of the cotinine test to research staff via text message, email, or postal mail.

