Power analysis. To demonstrate that this proposal has adequate sample size to detect meaningful amplitude changes in the continuous measures taken at the post-training laboratory sessions (Specific Aims 1 & 2), we conducted a power analysis using the G*Power program (v3.1.2; Heinrich Heine University, Düsseldorf, Germany). We calculated power to ensure that we could detect a significant 2-way (ABM intervention by time) ANOVA interaction for any of our continuous measures, as assessed at the baseline, 1-day post-training, and 8-weeks post-training sessions. If we assume a conservative Bonferroni-corrected Type I error rate of $\alpha=0.01$, 250 participants, moderately correlated within-subject observations ($r=0.5$), and a conservative nonsphericity correction ($\varepsilon=0.75$) we have 80% power to detect differences corresponding to a Cohen's f of 0.11 or larger for the 2-way interaction. Even if we were to experience an unlikely 30% attrition rate, we would have power to detect a Cohen's f of 0.13 or larger. According to Cohen [117], a Cohen's f of 0.10, 0.25, and 0.40 correspond to a small, medium, and large effect size, respectively, meaning that we have the power to detect a small effect size or greater on our continuous measures. To demonstrate that we would have adequate power to detect likely AB differences for Aim 1, we searched the literature for studies with a similar design to ours. Given that no previous study has evaluated the impact of multi-session ABM on AB in

smokers, we decided to estimate a likely effect size from the one alcohol study that used the MDP task for both multi-session ABM and the AB assessments [2]. We estimated a Cohen's *f* value for this study by taking the square root of the *F* ratio multiplied by the ratio of the degrees of freedom [117]. From this formula, we estimated a Cohen's *f* of 0.64, based on the reported *F* value for the significant ABM training group (ABM, sham) main effect, $F(1,23)=9.4$, $p<.01$. This Cohen's *f* value corresponds to a large effect size and is well within the range for which we have sufficient power to detect. We recognize that this alcohol study does not provide an ideal comparison for the effects sizes we will likely obtain, but it does suggest that ABM produces large effects on AB, effects which should be well within the power requirements of our study to detect.

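### Aim 1 names a subject random effect but no within-subject covariance, and neither continuous-outcome analysis carries the non-sphericity allowance used in the power calculation

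*Combined protocol and SAP*

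**What the plan says.** Section D, Statistical Approach & Expected Outcomes, describes the Aim 1 analysis as a two-group by three-session "linear mixed model using RT difference scores (neutral-cigarette) as the dependent measures and subject as the random effect". It is run separately for the dot-probe and Stroop difference scores. Residual covariance, estimation method, degrees of freedom and significance level are not stated.

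For the continuous smoking outcomes of Aim 2 the same section says "we will conduct mixed between-within repeated measures ANOVA", with the predictors and covariates of Aim 1. No sphericity correction is named.

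The Power analysis paragraph covers the continuous measures of both aims. It powers the group-by-time interaction at a Bonferroni-corrected α of 0.01 with 250 participants, a within-subject correlation of 0.5 and a "conservative nonsphericity correction" of ε = 0.75. It reports 80% power at Cohen's f = 0.11, or f = 0.13 with 30% attrition.

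Figure 2 puts the laboratory sessions on days 1, 15 and 72, with the quit date on day 16. The Aim 1 hypotheses cover both the change just after training and its persistence at 8 weeks.

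**The concern.** A random intercept with independent residuals gives every session the same variance and every pair of sessions the same correlation. That is compound symmetry, which implies sphericity. The change from baseline to 1 day and the change from baseline to 8 weeks then receive the same standard error, whatever the data show.

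The sponsor budgeted for departure from sphericity when sizing the trial, but the analysis text does not carry the allowance forward. Two things are at stake. The interaction test may reject more often than its stated level. The session contrasts, which answer the short-term and persistence hypotheses, may have standard errors that are too small or too large. Leaving the covariance open also means that it could be chosen after results are seen.

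**Working it through.** **Inputs.** From the Power analysis paragraph: N = 250, three sessions, α = 0.01, r = 0.5, ε = 0.75. From Figure 2: days 1, 15 and 72. Assumed here: 125 per arm (the allocation ratio is not stated), normal scores, complete data.

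**1. The plan's own figure.** With k = 2 groups and m = 3 sessions, λ = f²·N·m·ε/(1 − r), df1 = (k − 1)(m − 1)ε = 1.5 and df2 = (N − k)(m − 1)ε = 372. Solving for 80% power gives f = 0.108 at N = 250 and f = 0.129 at N = 175. These round to the stated 0.11 and 0.13. With ε = 1 and N = 250 the answer is 0.097, so the stated figure does rest on the correction.

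**2. Interaction test without correction.** The random-intercept test refers F to 2 and 496 degrees of freedom, with a 1% critical value of 4.65. Box's approximation evaluates that value under F(2ε, 496ε). Direct simulation draws the ratio of weighted chi-squares.

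| True ε | Nominal 1%: Box | Nominal 1%: simulated | Nominal 5%: Box | Nominal 5%: simulated |
|---|---|---|---|---|
| 1.00 | 1.0% | 1.0% | 5.0% | 5.0% |
| 0.90 | 1.3% | 1.3% | 5.6% | 5.4% |
| 0.75 | 1.8% | 1.9% | 6.5% | 6.3% |

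**3. Range for the 8-week contrast at ε = 0.75.** Let the covariance of the two orthonormal session contrasts have eigenvalues 1 ± d, scaled to mean 1. Then ε = 1/(1 + d²), so d² = 1/0.75 − 1 = 0.333 and d = 0.577. The model uses the mean eigenvalue (1) for every contrast, while the true value lies between 0.423 and 1.577. The ratio of model to true standard error therefore lies between:

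- 1/√1.577 = 0.80, with type I error at nominal 1% of 2Φ(−2.576 × 0.796) = 4.0%;
- 1/√0.423 = 1.54, with type I error of about 0.01%.

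The lower end applies when baseline and 8 weeks are the least correlated pair. The upper end applies when the post-training session is the odd one out.

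**4. One illustrative matrix.** Take unit variances and correlations of 0.75 (baseline/1-day), 0.50 (1-day/8-week) and 0.25 (baseline/8-week). The mean is 0.5 and ε is exactly 0.75. The change variances are 0.5 (1-day) and 1.5 (8-week), against a pooled value of 1.0.

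- 8-week ratio: √(1/1.5) = 0.82, so the standard error is 18% too small. The contrast rejects about 3.5% at nominal 1% and 11% at nominal 5%.
- 1-day ratio: √(1/0.5) = 1.41, so the standard error is 41% too large. For a 0.4 SD effect the true standard error is √(2 × 0.5/125) = 0.0894 and 0.4/0.0894 = 4.47. Power at 1% is Φ(4.47 − 2.576) = 97% with the true standard error and Φ(4.47 − 2.576 × 1.414) = 80% with the model's.

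**5. Decay with elapsed time.** Assume correlation q^(days/14) over gaps of 14, 57 and 71 days, with q from 0.6 to 0.9. Then ε runs from 0.83 to 0.69. The 8-week ratio runs from 0.89 to 0.83 (type I error 2.2% to 3.2% at nominal 1%), and the 1-day ratio from 1.35 to 1.70. If session-specific noise makes up half the variance, ε rises to 0.96–0.98, the 8-week ratio to about 0.95 and the 1-day ratio falls to 1.08–1.12.

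**6. After the change.** With an unstructured covariance (2 and 247 degrees of freedom), the simulated interaction test rejects 0.97% and 1.04% under two covariance patterns with ε = 0.75, and 1.01% under compound symmetry. An ε-adjusted F (critical value 5.40) rejects about 1.1% at ε = 0.75.

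**The case against.** The text names subject as the random effect but does not say that residuals are independent. The phrase may only identify the clustering unit, and it excludes no residual structure. This stands: the defect is an unstated covariance, not a declared sphericity assumption.

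The plan calls ε = 0.75 conservative, so it is a safety margin and not an estimate. A reader might infer that the sponsor believes sphericity to be false. The documents do not say that, and the inflation is conditional on the true ε. Nor does the analysis text commit to a 1% level, since α = 0.01 appears only in the Power analysis. The power paragraph also covers the Aim 2 measures, so the authors may have intended a corrected F there, although the Aim 2 text does not say so.

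The most tempting stronger reading is that the 8-week standard error is too small and the 1-day one too large. That does not follow from ε = 0.75, which does not identify the sessions that differ. No session-specific SDs or correlations are given for the reaction-time scores. Decay over days 1, 15 and 72 makes this direction plausible. Uneven response to 13 days of training could instead make the post-training session the odd one out, and the 8-week standard error would then be too large.

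Finally, an ε-adjusted F would also bring the interaction test close to its level. That is correct for the interaction, but it leaves the pooled standard errors of the session contrasts unchanged.

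**Conclusion.** The gap between the power assumption and the analysis text is real, and its severity is moderate. If Aim 1 is fitted as a plain random-intercept model and ε is 0.75, the nominal 1% interaction test runs at about 1.8 to 1.9%, nearly twice its level. With ε closer to 1 the excess is small or absent.

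The session contrasts are the more exposed part. At ε = 0.75 the 8-week standard error could be 20% too small or 54% too large, and the documents cannot settle which. The figures in step 4 illustrate one matrix and are not predictions. All results assume equal allocation, normal scores and complete data.

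The case for acting does not depend on knowing the direction of the error. A covariance that must be chosen anyway is better fixed in advance, in a form that is valid whichever way the sessions differ.

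**What to change.** State in the Aim 1 and Aim 2 analysis text that each continuous outcome is fitted with session as a repeated factor within subject, an unstructured covariance across the three sessions, REML estimation and Kenward-Roger degrees of freedom. State that the 1-day and 8-week group contrasts and their standard errors come from that model. Apply the same sentence to the Aim 2 outcomes in place of the uncorrected repeated-measures ANOVA. If the ANOVA is kept, name an ε-adjusted F for the interaction and a separate error term for each session contrast.

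The cost is a sentence or two of wording and four more covariance parameters (six in place of two), which is negligible with 250 participants.
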